10.2 Sample Size and Accrual

Sample size for this study is mainly determined by time and resource (budget) constraints. We will allocate 26 patients to the two groups (12 per group). We assume 20% of values will be missing or otherwise unusable, yielding complete data for 10 patients per group for analyses. As stated

above, estimation rather than statistical inference is our focus, and so it is not this project's goal to have adequate statistical power. We can focus instead on precision, and for the primary outcome of QOL (standardized), the half-width of a two-sided 95% confidence interval would be .9SD, assuming 10 patients per randomized group. We obtained this result using nQuery Advisor v7.0 software.

We claim such a study as feasible if and only if both (a) recruitment rate (p) is high enough and (b) retention rate (q) is sufficiently high, i.e., if both p and q are large enough. More specifically, this is to test the following hypothesis:

$$H_0: p \leq 50\% \text{ or } q \leq 50\% \text{ vs } H_1: p \geq 80\% \text{ and } q \geq 70\%.$$

Denote N as the number of eligible patients we try to recruit, and Y as the number of patients who are recruited, X as the number of patients (among the Y who are enrolled) who complete the PACT intervention. The target value of Y is 20, and we assume (1) N follows a negative binomial distribution, $NB(20, p)$, (2) X , conditional on ($Y = 20$), follows a binomial distribution $B(20, q)$. We further assume that N and X are independent. We list cut-offs and associated type I error and power under different N and X values for rejecting the hypothesis of $p \leq 50\%$ and the hypothesis of $q \leq 50\%$.

Recruitment (N: total number of patients being approached)

Y	Rejection Area	Type I error ($p \leq 50\%$)	Power ($p \geq 0.80$)
20	$N \leq 20+12$	0.108	0.994
20	$N \leq 20+13$	0.148	0.997
20	$N \leq 20+14$	0.196	0.999
20	$N \leq 20+15$	0.250	0.999

Retention (X: total number of patients who complete the intervention)

Y	Rejection Area	Type I error ($q \leq 50\%$)	Power ($q \geq 0.70$)
20	$X > 8$	0.748	0.995
20	$X > 9$	0.588	0.983
20	$X > 10$	0.412	0.952
20	$X > 11$	0.252	0.887

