Under the independence assumption, the overall Type I error rate is the product of two individual type I errors, and the overall power is the product of power of two individual powers. We will reject the hypothesis of $p \leq 50\%$ if $N \leq 34$, and reject the hypothesis of $q \leq 50\%$ if $X > 11$. The resulted overall type I error is 4.9%, while the overall power is 88.6%.

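### The overall type I error of the feasibility rule is given as 4.9%, but for the stated either-rate null it is the larger component error, 25.2%

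*Combined protocol and SAP*

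**What the plan says.** Section 10.2 sets up a joint test of the recruitment rate p and the retention rate q. Feasibility is claimed only when both are high enough. The null joins the two failures with *or*: "H_0: p \leq 50\% \text{ or } q \leq 50" (per cent). The alternative joins the two successes with *and*: p at least 80% and q at least 70%.

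The section states that "The target value of Y is 20". The number approached, N, is negative binomial with parameters 20 and p. The number completing, X, is binomial with parameters 20 and q. "We further assume that N and X are independent".

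Two tables give the component operating characteristics. For N ≤ 34 the type I error is 0.196 and the power 0.999. For X > 11 they are 0.252 and 0.887. These two cut-offs form the chosen rule. The section combines them as follows: "Under the independence assumption, the overall Type I error rate is the product of two individual type I errors", with power also taken as a product. It concludes: "The resulted overall type I error is 4.9%, while the overall power is 88.6" (per cent).

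**The concern.** The null covers every case in which at least one rate is unacceptable. The type I error of a rule that requires both tests to pass is the highest pass probability anywhere in that region. The product of the component errors describes only the point where both rates sit at 50%. That is not the worst case: if recruitment is excellent and retention is poor, the recruitment test passes almost automatically and only the retention test guards against a false claim.

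Feasibility is the primary objective and primary endpoint (Sections 3.1, 3.4 and 10.1), and Section 10.2 is the only place with a hypothesis test and stated error rates. A reader will take 4.9% to mean conventional control of a false verdict of feasible. If the true figure is five times as large, a positive verdict carries much less weight than the plan implies.

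**Working it through.** **Inputs, all from Section 10.2.** Y = 20; N ~ NB(20, p); X ~ Bin(20, q); N and X independent; rule N ≤ 34 and X > 11; null p ≤ 0.50 or q ≤ 0.50; alternative p ≥ 0.80 and q ≥ 0.70.

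**Component pass probabilities.** Twenty enrolments within 34 approaches means at least 20 successes in 34 trials, so

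- A(p) = P(N ≤ 34) = P(Bin(34, p) ≥ 20): A(0.5) = 0.1958 and A(0.8) = 0.9988.
- B(q) = P(X > 11) = P(Bin(20, q) ≥ 12): B(0.5) = 0.2517, B(0.7) = 0.8867 and B(0.75) = 0.9591.

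These agree with the tabulated 0.196, 0.999, 0.252 and 0.887.

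**The plan's own figures.** By independence, the probability of declaring feasibility at any (p, q) is A(p) × B(q).

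- At p = q = 0.5: 0.1958 × 0.2517 = 0.0493, the stated 4.9%.
- At p = 0.8, q = 0.7: 0.9988 × 0.8867 = 0.8856, the stated 88.6%.

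So the multiplication is right. What remains is whether p = q = 0.5 is the worst point of the null.

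**Worst case over the stated null.** A and B both increase with their arguments, and both equal 1 when the rate is 1. The null is the union of two regions:

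- p ≤ 0.5, any q: the maximum is A(0.5) × B(1) = 0.1958 × 1 = 0.1958.
- q ≤ 0.5, any p: the maximum is A(1) × B(0.5) = 1 × 0.2517 = 0.2517.

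The type I error is the larger, max(0.1958, 0.2517) = 0.2517, or 25.2%. A search over p and q in steps of 0.01 gave the same maximum. Relative to the stated value, 0.2517 / 0.0493 = 5.1.

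**Realistic points inside the null.**

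| Recruitment p | Retention q | Probability of declaring feasible |
|---|---|---|
| 0.50 | 0.50 | 0.1958 × 0.2517 = 4.9% |
| 0.80 | 0.50 | 0.9988 × 0.2517 = 25.1% |
| 0.50 | 0.70 | 0.1958 × 0.8867 = 17.4% |
| 0.50 | 0.75 | 0.1958 × 0.9591 = 18.8% |

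The 0.80 and 0.70 are the plan's own alternatives, and 0.75 is the retention target in Section 3.1. The high values are therefore not confined to an extreme corner.

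**When 4.9% would be right.** It is the type I error for a null in which *both* rates are at most 50%. Section 10.2 does not write that null, and no other section narrows the one it does write.

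**The case against.** Several points can be made for the plan.

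- *This is an estimation study.* Section 10.2 puts estimation ahead of inference, and Section 10.3 rules out formal significance testing. But the Section 10.3 statement belongs to the pre/post analysis of QOL, symptoms and function. Section 10.2 still gives hypotheses, cut-offs, an error rate and power for feasibility, so the error rate should be right.
- *The components are visible, and a pilot may tolerate 25%.* Both are fair. The 0.196 and 0.252 are tabulated, and Section 10.3 will report both proportions with 95% confidence intervals, which limits the harm. A tolerance of 25% should nevertheless be stated as 25%; the figure offered as the overall error is 4.9%.
- *Other success standards exist.* Section 3.1 asks for 60% enrolment and 75% retention. Read as cut-offs with 20 enrolled, these are N ≤ 33 and X ≥ 15, with component errors 0.148 and 0.021 and hence an overall 14.8%. That is a different rule from the one to which Section 10.2 attaches its error rate. It also exceeds 5%.
- *The model for X may not fit the trial.* Section 10.2 defines X as those completing PACT, yet only 10 of the 20 receive it. Read literally, X cannot exceed 10 and X > 11 can never happen. Section 10.3 measures retention among all enrolled, which suggests that all 20 count. This stands as a condition on the 25.2%, and the definition needs tidying. It does not support the 4.9%, which rests on the same binomial with 20 patients.

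**Conclusion.** The point holds. Under the plan's own models, null and cut-offs, the overall type I error is 25.2%, not 4.9%. The error is one of concept: the multiplication is correct, but it is applied to one point of the null rather than to its worst case. The power of 88.6% stands.

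The 25.2% is a ceiling, reached when retention is 50% and recruitment approaches 100%, and 25.1% is already reached at 80% recruitment. When recruitment is the failing rate at 50%, the ceiling is 19.6%. These figures assume that all 20 enrolled patients count towards X and that N and X are independent, as Section 10.2 states.

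**What to change.** In Section 10.2, keep the product for power and change the type I error statement. Suggested text: *Because the null holds when either rate is unacceptable, the overall type I error is the larger of the two component errors: 25.2% for N ≤ 34 and X > 11. When both rates equal 50% the probability of declaring feasibility is 4.9%. Overall power is 88.6%.* State in the same place that X counts completion among all 20 enrolled, if that is the intention.

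This costs one sentence and a less favourable number. It changes no cut-off and needs no extra patients.

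If the sponsor wants tighter control, both components must meet the chosen level, and power at p = 80%, q = 70% falls:

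| Enrolled | Rule | Component errors | Overall error | Power |
|---|---|---|---|---|
| 20 | N ≤ 34, X > 11 | 0.196, 0.252 | 25.2% | 88.6% |
| 20 | N ≤ 32, X > 12 | 0.108, 0.132 | 13.2% | 0.9939 × 0.7723 = 76.8% |
| 20 | N ≤ 30, X > 14 | 0.049, 0.021 | 4.9% | 0.9744 × 0.4164 = 40.6% |
| 26 | N ≤ 40, X > 17 | 0.040, 0.038 | 4.0% | 0.9921 × 0.6274 = 62.2% |

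With 20 enrolled, X > 13 just misses 5% (0.058). Even if all 26 patients mentioned in Section 10.2 were counted, 5% control would not preserve the stated power. Reporting 25.2% openly is a reasonable choice for a pilot; tightening the rule is optional.

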3.0 STUDY OBJECTIVES/ENDPOINTS

3.1 Primary Objective

Determine feasibility and acceptability of study methods and examine changes in pre- and post-treatment measures of function, patients' self-report of symptoms and QOL, and patients and caregivers' post self-report of readiness for discharge. We will include 10 control and 10 intervention patients.

Feasibility: We plan enrollment of 60% of those approached; achieve 75% retention rate, 75% of intended data collection; and no intervention-related adverse events. The PACT intervention team will have a reduced workload; we will record effort required to deliver the PACT intervention. These feasibility data will inform if, or to what extent, workload is affected to plan future studies and implementation. The team will receive 32 hours of training in palliative care and adaptive leadership approaches. Adherence will be monitored by electronic tracking from OT and PT notes and by self-report.

Acceptability: Assessed by interviews and surveys with patients and their caregivers about their experiences.

Changes in pre-and-post QOL, symptoms, and function: Compare changes between control and intervention.

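### Sections 3.1 and 10.2 use different recruitment and retention rates: the 88.6% power applies at 80%/70%, while at the 60%/75% in 3.1 the feasibility rule passes only about 60% of the time

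*Combined protocol and SAP*

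**What the plan says.** Section 3.1 (Primary Objective), under feasibility: "We plan enrollment of 60% of those approached; achieve 75% retention rate, 75% of intended data collection". The same list also asks for no adverse events related to the intervention.

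Section 10.2 (Sample Size and Accrual) makes feasibility depend on recruitment rate p and retention rate q both being high enough. The null is that either rate is at most 50%. The alternative is p of at least 80% together with q of at least 70%. On the model: "The target value of Y is 20", and "N follows a negative binomial distribution" with parameters 20 and p. The number retained, X, is binomial with 20 trials and probability q, independent of N. The recruitment table is headed "Recruitment (N: total number of patients being approached").

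The chosen cut-offs are N ≤ 34 and X > 11, and the section concludes: "The resulted overall type I error is 4.9%, while the overall power is 88.6" per cent.

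**The concern.** The two sections describe the same quantities. The 60% in 3.1 is a share of those approached, and N in 10.2 counts those approached. Retention in 3.4.1 is the share of consented patients who complete the intervention, and X in 10.2 counts completers among the enrolled. Yet the rates differ on both components: 60% against 80% for recruitment, and 75% against 70% for retention. No section gives a basis for 80% or explains why power is quoted away from the 3.1 rates. Section 5.1 points, if anything, towards caution about recruitment.

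Feasibility is the primary endpoint, and 10.2 decides it with a binary rule. Someone who reads 3.1 for the plan and 10.2 for the power would take about an 11% risk (1 − 0.886) of a negative verdict if the plan is met. Someone who reads 3.1 as the standard for success would expect 10.2 to enforce it. The first reader gets the wrong risk; the second finds that the rule does not enforce the standard. With two standards in one protocol, the choice between them could be made after the data are seen.

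**Working it through.** **Inputs.** Y = 20; N ~ NB(20, p); X ~ B(20, q); N and X independent; cut-offs N ≤ 34 and X > 11; null 50%/50% and alternative 80%/70% (all from 10.2). Planned rates 60%/75% (3.1).

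**Formulas.**
- Recruitment: P(N ≤ 34 | p) = P(at most 14 refusals before the 20th enrolment) = P(Bin(34, p) ≥ 20).
- Retention: P(X > 11 | q) = P(Bin(20, q) ≥ 12).
- Overall: the product of the two, as 10.2 specifies.

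**Step 1: reproduce the plan's figures.**

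| Quantity | Recruitment | Retention | Product | Plan states |
|---|---|---|---|---|
| p = q = 50% | 0.1958 | 0.2517 | 0.0493 | 4.9% |
| p = 80%, q = 70% | 0.9988 | 0.8867 | 0.8856 | 88.6% |

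Both agree to the printed precision, so the model used below is the plan's own.

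**Step 2: the same rule at other rates, with retention at the planned 75%.** P(X > 11 | 0.75) = 0.9591.

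| Enrolment rate p | P(N ≤ 34) | Chance of declaring feasibility at q = 75% |
|---|---|---|
| 60% (section 3.1) | 0.6274 | 0.6274 × 0.9591 = 0.602 |
| 65% | 0.8257 | 0.8257 × 0.9591 = 0.792 |
| 70% | 0.9429 | 0.9429 × 0.9591 = 0.904 |

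At the 3.1 rates the risk of a negative verdict is 1 − 0.602 = 0.398, against 1 − 0.886 = 0.114 at the design alternative. The loss comes entirely from recruitment, which falls from 0.999 to 0.627. Retention improves, from 0.887 at 70% to 0.959 at 75%.

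**Step 3: read 60% and 75% as thresholds on the observed rates.**
- Recruitment: N = 34 passes, and 20/34 = 58.8% is below 60%. N = 33 gives 20/33 = 60.6%. The conflict is therefore confined to the single value N = 34 and amounts to 60 − 58.8 = 1.2 percentage points.
- Retention: X = 12 passes, and 12/20 = 60%. Meeting 75% needs 15 of 20. For X = 12, 13 or 14 the rule passes while the 3.1 figure is missed; at X = 12 the gap is 15 percentage points.

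**Step 4: the obvious patch, N ≤ 33 alone.** P(N ≤ 33 | 0.60) = 0.547, so the chance of passing at 60%/75% becomes 0.547 × 0.959 = 0.525. At 80%/70% it is 0.997 × 0.887 = 0.884. The patch removes the small recruitment conflict, leaves the larger retention conflict, and lowers the chance of passing at the planned rates.

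**The case against.** The strongest reply is that nothing is miscalculated. Section 10.2 writes out its alternative and labels its power columns with 80% and 70%, so a careful reader knows what the 88.6% refers to. That stands: a reader might infer that the 88.6% is an arithmetic error, and it is not.

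A second reply is that the 3.1 figures read as benchmarks, since they sit in a list with the adverse-event criterion. If 60% is a minimum acceptable rate, a study whose true rate lies exactly there need not pass with high probability, and quoting power at a better rate is normal practice. This also has force. A reader might infer that a study performing as planned would fail about 40% of the time. That follows only if 60% and 75% are expected rates, and 3.1 does not say which they are. But the threshold reading does not reconcile the sections either, because the rule then admits results that 3.1 counts as short, chiefly on retention. The two readings are alternatives, and their consequences should not be added together.

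Third, 10.2 says that estimation is the focus, that sample size follows from time and budget, and that adequate power is not a goal. Section 10.3 reports enrolment and retention with 95% confidence intervals, so readers can judge the targets for themselves. This lowers the stakes, since no enrolment number depends on the 88.6%. It does not remove the point. The disclaimer leads into the precision statement for QOL, and the next paragraph sets a formal pass/fail rule with its own error rate and power.

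**Conclusion.** The inconsistency is real and should be fixed; it is moderate in weight. Sections 3.1 and 10.2 use different rates for both recruitment and retention, without explanation. If 60%/75% are expected rates, the rule declares feasibility about 60% of the time there, not 88.6%. The result is sensitive to recruitment: 0.79 at 65%/75% and 0.90 at 70%/75%. If they are success thresholds, the rule is looser than 3.1, slightly on recruitment (58.8% passes) and materially on retention (60% passes against 75%).

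The figures rest on the plan's own model taken as written: 20 enrolled, negative binomial N, binomial X out of 20, and independence. A reader might conclude that the N ≤ 34 cut-off is the main fault. The numbers do not support that, because it conflicts with 3.1 at one value only.

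**What to change.** In 10.2:
- State the chance of passing at the 3.1 rates (about 60% at 60%/75% with the current cut-offs) next to the 88.6%, and say that the 88.6% applies only at 80%/70%.
- State whether 60% and 75% are expected rates or success thresholds.

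In both sections, use one set of rates for recruitment and for retention. If 80%/70% is what the sponsor expects, change 3.1 to match and give the basis.

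Do not tighten only the recruitment cut-off to N ≤ 33. If any cut-off is changed, recompute and restate every error and power figure, including the chance of passing at the 3.1 rates.

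The cost is a few sentences and no extra patients. The downside is that the stated power looks less favourable.

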10.3 Data Analysis Plans

Feasibility Data Management and Analysis

Data will be collected on feasibility metrics. These include collecting and recording data on all patients approached for recruitment, along with an indicator of whether each patient is enrolled or not. The proportion of those enrolling, along with its 95% confidence interval, will be

computed. Of those enrolled, we will record whether there is attrition prior to each patient's end of follow-up, as well as the reasons for such attrition. The proportion of those retained, along with its 95% confidence interval, will be computed as 1 minus the proportion who experienced attrition from the study. The frequency of data values will also be tracked, and the proportion of non-missing data values, along with its 95% confidence interval, will be computed. The frequency and type of adverse events, including intervention-related adverse events, will be recorded. Staff hours reflecting the effort required to deliver the intervention to each patient enrolled into the intervention arm will be tracked; its mean and standard deviation will be computed across patients.

Acceptability Data Management and Analysis

Interviews will be transcribed by a professional transcription agency. Using Atlas.ti for analysis, Drs. [name] and [name] will read transcripts to derive codes. They will review and discuss labels to group codes into related categories and identify major themes through this process. After we define each major theme, we will identify corresponding exemplar quotes. We will address trustworthiness of analysis procedures and findings through creation of an audit trail to record data collection, coding, and analysis decisions. The interviewer ([name]) will make reflexive memos after each interview and review memos with corresponding audio recordings to discern linkages, gaps, and questions. When the two coders do not agree on their initial code, code negotiation and transcript review will occur.

Analysis of Change in Pre-and-Post QOL, Symptom, and Function

Analyses will be conducted following an intention to treat approach, such that patients are analyzed as allocated. Descriptive statistics will be computed on all analysis variables at each time point separately for each condition. These values will be compared between the conditions at baseline to determine whether any imbalanced. These include means and standard deviations for continuous variables, and frequencies and percentages for categorical variables. As the primary analysis of pre and post values, we will fit an analysis of covariance (ANCOVA) model for each post outcome, with a main effect for group (intervention versus control) while controlling for the covariate of the corresponding baseline (pre) value. Sensitivity analyses will repeat this ANCOVA but adding demographic variables that are imbalanced at baseline, subject to sufficient sample size. This approach will allow us to assess whether the mean post values differ between groups for each measure through the regression coefficient for the main effect of group, as well as its 95% confidence interval. This information will be useful in planning for the subsequent R01, and we will calculate effect sizes for the post measure as the ratio of the mean difference between the intervention and the control groups to its standard deviation. For measures where more than one follow-up measure is collected, this approach can be extended through a linear mixed effects model approach to repeated measures analysis, and within-patient correlation can be estimated. If extensive (e.g., greater than 10%), multiple imputation will be considered for missing values. No formal significance testing will occur, as the intention is to evaluate and estimate effect sizes rather than formal hypothesis testing, and hence multiplicity is not a concern from this perspective.

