2.0 STUDY PURPOSE AND DESIGN

This is a single institution, feasibility trial of 20 (10 control and 10 intervention) patients with the primary objective of assessing feasibility, acceptability, and change in pre and post measures of symptoms, function, and QOL by administering the PACT intervention.

Study subjects will be identified by the Study Coordinator through pre-screening through the electronic health record after being referred by the oncologists and pharmacists. Eligible patients will be approached by the Study Coordinator to confirm eligibility, which includes requesting permission of the patient's attending physician. Seven days prior to and within three days after initiation 1st cycle HMA or low-dose cytarabine + VENE, written informed consent will be obtained (A total of 10 days of recruitment period and baseline assessment).

First, ten participants in the control group will receive usual care. After the control patients have completed the study, then 10 intervention participants will receive the PACT intervention, a novel symptom management intervention, which aims to build patient skills to manage AML treatment-related, and chronic illness symptoms. Because patients receive chemotherapy during the first 7 days of hospitalization or clinic visit, the intervention will start at day 1 or day 2 of chemotherapy. During hospitalization, the PACT RN will assess AML symptoms daily (using PRO-CTCAE), and PACT OT and PT will assess function at baseline (day 1 or 2), days 3 or 4, and days 6 or 7. This study uses UNC hired staff of RNs, OTs, and PTs to deliver the intervention.

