3.4 Primary Endpoint

3.4.1 Feasibility will be defined as: % approached, retention rate (% of consented patients who completed the intervention); % intended data collection, safety (# of adverse events).

3.4.2 Adherence will be monitored by electronic tracking from OT and PT notes and by self-report during the intervention.

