10.0 STATISTICAL CONSIDERATIONS

10.1 Study Design

This is a pilot clinical trial of the PACT intervention in older adults with AML. The primary objective is to assess the feasibility (recruitment and retention) and acceptability of PACT intervention and examine change in pre and post measures of symptoms, function, and QOL comparing 10 control and 10 intervention patients with AML.

Qualitative research does not necessarily predict what might occur, but helps to understand in depth the characteristics of the situation and the meaning brought by participants and what is happening to them at that moment.

Interviews will be semi-structured, face to face with follow-up questions and probes to facilitate a deeper understanding of the patient, caregiver perceptions of the intervention. Interviews will take place on 4 oncology in patient's hospital room or private clinic room and will not last longer than one hour. An interview guide, developed in advance of data collection, will be used to provide a structure to the process (Appendix 13.1).

The interview prompts will focus on the overall perception of the PACT intervention. Each interview will be digitally audio-recorded. Brief field notes will be made before, during (in a non-discrete manner) and after the interviews to make note of points thought to be relevant at the time.

Pseudonyms will be used to protect the identity of the participants. The pseudonym will be linked to demographic and clinical information in a master log. The master log of study participants' names and study codes will be kept in a secure file cabinet in the investigator's locked office.

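### The retention half of the feasibility rule does not measure retention under PACT: read literally, X > 11 cannot be reached, and counted as in section 10.3 it pools usual-care controls with PACT patients

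*Combined protocol and SAP*

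**What the plan says.** Section 10.1 states the aim as to "assess the feasibility (recruitment and retention) and acceptability of PACT intervention". Section 2.0 sets out two consecutive groups: "First, ten participants in the control group will receive usual care", and then "After the control patients have completed the study, then 10 intervention participants will receive the PACT intervention". Only the second ten are ever offered PACT.

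Retention is then defined in three places.

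- **Section 3.4.1** (primary endpoint): "retention rate (% of consented patients who completed the intervention".
- **Section 10.2** (decision rule): "The target value of Y is 20". X is described in words as the enrolled patients who complete PACT, but is modelled as one binomial on all 20 with a single rate q. The null is q at or below 50% and the alternative is 70% or more. The null is rejected when X exceeds 11. The plan tabulates type I error 0.252 and power 0.887, and combines this with the recruitment condition N ≤ 34 for a joint error of 4.9% and power of 88.6%.
- **Section 10.3** (analysis): among those enrolled, attrition before the end of follow-up is recorded, and "The proportion of those retained, along with its 95% confidence interval, will be computed as 1 minus the proportion who experienced attrition from the study". Nothing here separates the groups.

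No retention criterion specific to the PACT group appears anywhere, and no retention rate is assumed for controls.

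**The concern.** Retention is one of only two inputs to a conclusion that section 10.2 words as holding if and only if both conditions are met. The count feeding that rule should therefore be unambiguous and should bear on the intervention under study.

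The wording in 3.4.1 and 10.2 restricts the count to patients who finish PACT, while the binomial on 20 and the cut-off of 12 make sense only if all 20 patients can count. The 10.3 definition does let all 20 count, but it then mixes patients who had PACT with patients who did not.

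A common rate for the two groups is an assumption that the plan does not defend. PACT adds nurse, OT and PT contacts and twice-weekly calls, so retention could differ from usual care in either direction. What is at stake is whether the feasibility verdict, and the retention estimate carried forward to the planned R01, say anything definite about PACT.

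**Working it through.** **Inputs.** Ten controls and ten PACT patients (section 2.0). Y = 20, X > 11 (at least 12), q = 50% against 70%, N ≤ 34, p = 50% against 80% (section 10.2). Control retention is not given, so a range of 50% to 100% is assumed.

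**1. The plan's own figures.**
- Retention: P(B(20, 0.5) ≥ 12) = 0.2517 and P(B(20, 0.7) ≥ 12) = 0.8867 (stated 0.252 and 0.887).
- Recruitment: P(N ≤ 34) = P(B(34, p) ≥ 20) = 0.1958 at p = 0.5 and 0.9988 at p = 0.8 (stated 0.196 and 0.999).
- Products: 0.1958 × 0.2517 = 0.0493 and 0.9988 × 0.8867 = 0.8856 (stated 4.9% and 88.6%).

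All reproduce. They describe one common q for all 20 patients.

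**2. Literal reading (3.4.1 and the words of 10.2).** Controls cannot complete PACT, so X is the number of PACT completers and is at most 10. Hence P(X ≥ 12) = 0 for every value of PACT retention, including 100%.

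**3. Attrition reading (10.3).** Let C ~ B(10, q_C) be controls retained and I ~ B(10, q_I) PACT patients retained, independent, with X = C + I. Then P(X ≥ 12) = Σ_c P(C = c) · P(I ≥ 12 − c).

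The number of PACT patients needed is 12 − c: 2, 3, 4 or 5 of 10 when 10, 9, 8 or 7 controls are retained. In the extreme case of 10 controls and 2 PACT patients, the exact 95% interval for PACT retention is 2.5% to 55.6%.

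Pass probability with true PACT retention q_I = 50%:

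| Control retention | 50% | 60% | 70% | 75% | 80% | 90% | 100% |
|---|---|---|---|---|---|---|---|
| P(X > 11) | 0.252 | 0.414 | 0.597 | 0.688 | 0.774 | 0.912 | 0.989 |

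The last entry can be checked by hand: P(I ≥ 2) = 1 − (1 + 10)/1024 = 0.989. The probability exceeds one half only when control retention is above about 64.8%. With true PACT retention of 20%, it is 0.10, 0.37 and 0.62 at control retention of 70%, 90% and 100%.

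**4. A condition on the PACT patients alone.** X_PACT ~ B(10, q), with N ≤ 34 kept and the plan's product method used for the joint figures (× 0.1958 for error, × 0.9988 for power):

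| Cut-off | Error at 50% | Power at 70% | Joint error | Joint power |
|---|---|---|---|---|
| ≥ 6 of 10 | 386/1024 = 37.7% | 85.0% | 7.4% | 84.9% |
| ≥ 7 of 10 | 176/1024 = 17.2% | 65.0% | 3.4% | 64.9% |
| ≥ 8 of 10 | 56/1024 = 5.5% | 38.3% | 1.1% | 38.2% |

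The 75% target in section 3.1 corresponds to 7.5 of 10, that is, at least 8.

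**The case against.** The strongest reply is that section 3.1 frames the primary objective as feasibility of the study methods, and 10.2 speaks of the study being feasible. Both groups undergo the same assessment battery, so retention over all 20 is a fair measure of whether the study can be run. This stands: pooled retention is worth reporting. It does not rescue the rule, because 3.4.1 and the words of 10.2 tie retention to completing the intervention.

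Second, a reader might infer that the plan would pass PACT with 2 of 10 retained, or would usually pass it at 50% retention. The documents do not support either as a statement of the plan. Section 10.3 never mentions X, q or the cut-off. The result appears only when its attrition-based count is put into the 10.2 threshold, and the literal X gives the opposite consequence. The 2-of-10 case also needs every control retained, and passing more often than not needs control retention above about 65%. Lower values are conceivable, since section 9.4 lists disease and treatment complications as grounds for removal in either group.

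Third, setting these pass probabilities against 0.252 changes the null. With controls at 90% to 100% and PACT at 50%, average retention is 70% to 75%, which lies in the plan's alternative for a common q. Passing there is an error only against a null specific to PACT.

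Finally, adherence tracking, reasons for attrition, adverse events, staff hours and interviews would all show problems with PACT. They would, but none of them enters the 10.2 rule.

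**Conclusion.** The concern holds in a limited form. On neither available reading does the retention condition measure retention under PACT: on one it cannot be met, and on the other it tests an average over two groups. On the pooled reading, with PACT retention at 50%, the pass probability is anywhere from 25% to 99% over control retention of 50% to 100%, so the plan's 0.252 and 0.887 apply only under a common q.

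The finding rests on 10 patients per group within Y = 20, as in sections 2.0 and 10.2. Section 10.2 also mentions 26 patients and 12 per group. If 12 PACT patients could count, the literal rule would need all 12 to complete, with probability 0.7^12 = 0.014 at q = 70%, so the conclusion would hardly change. The pooled figures also assume independent patients and an assumed control rate. What cannot be said is that the plan as written favours passing PACT.

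**What to change.** 1. Reconcile sections 3.4.1, 10.2 and 10.3 on one definition of retention, stating the event (completing PACT, or no attrition before the end of follow-up), the group and the denominator.
2. In 10.3, report retention with an exact 95% interval separately for the control and PACT groups. Keep the pooled proportion as a descriptive study-methods metric, and state to which group the 75% target in 3.1 applies.
3. In 10.2, rest the retention condition on the PACT patients. Choose and state one cut-off, and restate the individual and joint error and power for that denominator. The table in the working gives the options for 10 PACT patients; if 12 per group are enrolled, the figures must be recalculated.

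**Cost.** No new patients or data: group and attrition are already recorded. The change alters a primary decision rule, so it needs a protocol amendment and IRB approval under section 11.6. The stated figures become less favourable (for example, retention power of 65.0% with at least 7 of 10, in place of 88.7%), and the interval for 10 patients is wider than for 20. That loss reflects what ten PACT patients can show.
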